5.3 REPORTING PROCEDURES

All adverse events should be reported. Depending on the nature of the event the reporting procedures below should be followed. Any questions concerning adverse event reporting should be directed to the Chief Investigator in the first instance.

5.3.1 Non serious AEs

All such events, whether expected or not, should be recorded.

Mechanistic Evaluation of Treatments for Acute Antibody-Mediated Rejection of the Kidney Transplant (M.O.T. AMR) – Version 1.4 27/05/2020

5.3.2 Serious AEs

An SAE form should be completed and faxed to the Chief Investigator within 24 hours. However, relapse and death due to transplantation, and hospitalisations for elective treatment of a pre-existing condition do not need reporting as SAEs.

All SAEs should be reported to the South West -Frenchay Research Ethics Committee where in the opinion of the Chief Investigator, the event was:

- 'related', ie resulted from the administration of any of the research procedures; and
- 'unexpected', ie an event that is not listed in the protocol as an expected occurrence

Reports of related and unexpected SAEs should be submitted within 15 days of the Chief Investigator becoming aware of the event, using the NRES SAE form for non-IMP studies. The Chief Investigator must also notify the Sponsor of all SAEs.

Local investigators should report any SAEs as required by their Local Research Ethics Committee, Sponsor and/or Research & Development Office.

Contact details for reporting SAEs

[contact]

6. ASSESSMENT AND FOLLOW-UP

Assessment and follow-up of subjects is part of the TAR:GET-1 trial.

7. STATISTICS AND DATA ANALYSIS

The patient cohort size is dictated by TAR:GET-1: 170 patients, 85 in each arm. Under plausible modelling assumptions, for any biomarker that is on the mechanistic pathway between treatment and primary outcome, the power of the main study (90%) will be matched or exceeded when comparing the mean biomarker values between treatment groups. The mediation analysis will estimate for each biomarker the influence on allograft survival rate per unit change in biomarker, above and beyond, the direct effect of treatment. This will decompose the overall, marginal, treatment effect into a proportion attributable to a mechanism via the biomarker, and the complement attributable to direct effects, or other mechanisms. A similar multivariable analysis will proceed to estimate the mediation effects of multiple biomarkers acting in parallel, as an exploratory analysis using variable selection methods to control for over-fitting.

Data from this research project will be merged and linked with data from the TAR:GET-1 clinical trial by the statistician team.

Descriptive data

Mechanistic Evaluation of Treatments for Acute Antibody-Mediated Rejection of the Kidney Transplant (M.O.T. AMR) – Version 1.4 27/05/2020

This will include description of all the biological characteristics analysed in 2 populations (rituximab + SOC and SOC) at baseline and at all follow-up time points. Summary statistics (mean, median, SD, range for continuous variables, and frequency tables for categorical variables) will be reported broken down by treatment, with exploratory figures (box-and-whisker plots for continuous, and stacked bar-charts for categorical).

Outcome analysis

Appropriate measures of differences between treatment groups will be estimated with point estimates, 95% confidence intervals, and p-values. Depending on the type of variable (continuous, categorical, time-to-event), regression techniques (linear, logistic, cox) and transformation of the endpoints will be considered.

Differences in characteristics comparing pre- to post-treatment samples at sequential time points will be analysed comparing the 2 groups of patients (SOCR versus SOC) using mixed effect models repeat measurement techniques.

Mediation analysis, a special case of regression analysis, will be used to document that the treatment effects a change in the biomarker. We will use mediation analysis models to decompose total effect of treatment effect on graft loss into an indirect effect, which measures how much of the effect acts through the intermediate variable(s), and a residual direct effect. All the mediation analyses will be based on the Intention-to-Treat principle. We will fit the same form of outcome models as for the efficacy analyses, including the mediator as a covariate. We will use the mediation package within R which was developed specifically to make valid causal inference in explanatory analyses of the mechanisms of treatment-induced change in clinical outcomes in randomised clinical trials. All estimates of treatment differences will be summarised using effect size estimates and 95% confidence intervals (Dunn 2013). Collaborator for mediation analysis: [name], Professor of Statistical Methods for Medicine, UCL

Data and all appropriate documentation will be stored for a minimum of 10 years after the completion of the study, including the follow-up period.

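### Section 7 gives every biomarker on the pathway at least 90% power, but for a partial mediator this is not assured: it depends on the share of effect carried relative to the marker's correlation with outcome

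*Protocol*

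**What the plan says.** Section 7 of the protocol takes the sample size from the parent trial: "The patient cohort size is dictated by TAR:GET-1: 170 patients, 85 in each arm". It then makes its only power statement. The statement opens with a qualifier, "Under plausible modelling assumptions", and continues "for any biomarker that is on the mechanistic pathway between treatment and primary outcome, the power of the main study (90%) will be matched". The test concerned is the arm comparison of the marker, not the test of the indirect effect: the power is said to be "matched or exceeded when comparing the mean biomarker values between treatment groups". The assumptions are not listed. No marker effect size, standard deviation, marker-outcome correlation or share mediated is given.

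The same paragraph describes what the mediation analysis should find. The treatment effect is to be divided into "a proportion attributable to a mechanism via the biomarker, and the complement attributable to direct effects, or other mechanisms", and an exploratory analysis will "estimate the mediation effects of multiple biomarkers acting in parallel". The secondary objective in Section 2 likewise allows for a residual direct effect.

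**The concern.** Being on the causal pathway does not set a lower limit on how far the arms differ in the marker. A marker can be a true mediator, carry a modest part of the benefit, and show an arm difference that is harder to detect than the difference in graft loss. The power sentence covers any pathway marker, yet the paragraph around it plans for markers that carry only part of the effect.

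The arm comparisons of markers are the primary objective (Section 2), and Hypothesis 2 and the interest in surrogate endpoints (Section 1.2) lean on them. If a reader takes the 90% at face value, a non-significant marker difference looks like well-powered evidence that the marker is off the pathway. For a marker with p well below r, that inference would often be wrong.

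**Working it through.** **Inputs from the protocol (Section 7).** 85 patients per arm; 90% power for the main study; the comparison is of mean marker values between arms.

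**Assumptions.** Two-sided 5% test (the protocol gives no alpha, but reports 95% intervals); marker measured in all 170 patients; unadjusted two-sample t-test; linear mediation model with no treatment-by-marker interaction and no marker-outcome confounding. The shares p and correlations r are illustrative.

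**The plan's own figure.** The main trial's 90% cannot be rebuilt, because this protocol gives no graft-loss rates, hazard ratio, alpha or dropout. It is taken as given and converted to a standardised effect at 85 per arm:

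d_Y = (1.960 + 1.282) / √(85/2) = 0.497 by the normal approximation, or 0.500 by the t-test.

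**Relation between marker and outcome.** Let M = aT + u and Y = c′T + bM + e, with total effect τ = c′ + ab. Write s_M and s_Y for the within-arm standard deviations.

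- Share mediated: p = ab/τ, so a = pτ/b.
- Within-arm correlation: r = b·s_M/s_Y, so b = r·s_Y/s_M.
- Marker difference: d_M = a/s_M = (p/r)·(τ/s_Y) = (p/r)·d_Y.

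Marker power is therefore at least 90% exactly when p ≥ r. With p = 1 this holds for every r. With p < 1 it depends on r.

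**Results at 85 per arm, d_M = 0.500 × p/r.**

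| Share p | Correlation r | d_M | Power |
|---|---|---|---|
| 1.00 | 0.8 | 0.625 | 98% |
| 1.00 | 1.0 | 0.500 | 90% |
| 0.50 | 0.3 | 0.833 | above 99% |
| 0.50 | 0.5 | 0.500 | 90% |
| 0.50 | 0.6 | 0.417 | 77% |
| 0.25 | 0.2 | 0.625 | 98% |
| 0.25 | 0.3 | 0.417 | 77% |
| 0.25 | 0.4 | 0.313 | 53% |
| 0.25 | 0.5 | 0.250 | 37% |

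**Simulation check.** With 10,000 trials per setting, marker power and outcome power were 90% and 90% at p = 0.5, r = 0.5; 63% and 90% at p = 0.5, r = 0.7; and 36% and 90% at p = 0.3, r = 0.6.

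**Binary outcome.** Graft loss at 4 years is not a continuous variable. In a liability-threshold version, the control loss rate is assumed and the treated rate is set to give 90% power at 85 per arm, with r on the latent scale.

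- Control loss 30%: treated 10.3%, latent difference 0.740, break-even p/r = 0.497/0.740 = 0.67.
- Control loss 60%: treated 35.5%, latent difference 0.626, break-even p/r = 0.497/0.626 = 0.79.

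Over this range, p = 0.3 with r = 0.6 has 53% to 68% power, while p = 0.5 with r = 0.6 has 93% to 98%.

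**The case against.** The sentence is conditional. One assumption that would make it true is p ≥ r, and a plan not shown here may spell it out. This has some force: the protocol does not promise 90% without condition. But no condition is named, and any condition that rescues the sentence also removes the word 'any'.

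The linear model with an unadjusted t-test is not the planned analysis. A binary outcome lowers the break-even, as shown. The planned mixed models use pre-treatment values, and if baseline and follow-up correlated at 0.6 (an assumption), adjustment would raise the 77% entries to about 92% and the 37% entry to about 53%. Both points favour the protocol and narrow the region of failure, but neither rescues a marker with a low p/r.

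No section says that a non-significant marker will be declared off the pathway; estimates with 95% intervals are planned. That stands: the misreading is a risk that the power sentence invites, not a stated decision rule.

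A reader might infer that the power fails for partial mediators as a class. The documents do not support this. Partial mediators with p ≥ r keep 90% or more, and the protocol gives neither quantity for any marker.

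**Conclusion.** The point holds in limited form. The 90% figure is stated more broadly than the design supports. It is assured regardless of correlation only for a marker carrying the whole effect. For a partial mediator it fails when p is sufficiently below r: p < r in the linear working model, and p/r below about 0.67 to 0.79 for a binary outcome with assumed control graft loss of 30% to 60%. The shortfall can be large (37% at p = 0.25, r = 0.5 in the linear model) or absent (98% at p = 0.25, r = 0.2).

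How many planned markers are affected cannot be determined from the protocol. All power figures are illustrative and rest on the assumptions listed above. The point does not depend on incomplete sampling, which is a separate matter. Because the cohort size is fixed by the parent trial, this is a correction to a stated property and not a fault in the design.

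**What to change.** Replace the sentence on any pathway biomarker in Section 7 with wording such as: *With 85 patients per arm and a marker measured in all of them, a two-sided 5% comparison has 90% power for a standardised mean difference of 0.50. A marker carrying the whole treatment effect will meet this. A marker carrying only part of it may not, depending on the share it carries relative to its within-arm correlation with outcome. A non-significant marker difference does not exclude the marker from the pathway.*

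A short table of power by p and r, labelled illustrative and with its assumptions stated, would help. The cost is wording only: no change to sample, conduct or analysis. The stated power becomes less favourable for some partial mediators.

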Serial measurements of the strength of DSA and severity of biopsy features have been used to describe the natural history of AAMR and to determine response to treatments, including rituximab. There is evidence in the literature that treatment of AAMR may reduce antibody strength and/or affect complement-activating ability (Cioni 2018, Viglietti 2018b, Bailly 2018, Lefaucheur 2018) and may have a positive effect on biopsy scores (Viglietti 2018a, Sautenet 2016, Eskandary 2018, Choi 2017) or transcript levels (Eskandary 2018, Lefaucheur 2018). Immunosuppression can induce changes in B cell gene expression and functional profile (Banham 2018). However, the evidence is inconclusive and in places contradictory, and has not been validated in the context of randomised controlled trials. Therefore, serial measurements are not yet used to guide treatment decisions.

3) The need for surrogate endpoints for clinical trials in AMR

Given that the end point for trials in AAMR (graft loss) is remote, development of surrogate end points for AAMR trials is a priority (Velidedeoglu 2018). Longitudinal assessment of biomarkers in patients with AAMR has been shown to assist in outcome prediction, but here again data is limited (Viglietti 2018a). This project provides an opportunity to investigate potential surrogate markers of outcome.

This MOT-AMR research proposal has 2 hypotheses:

Hypothesis 1: AMR is a heterogeneous disease, with outcome and response to treatment accurately predicted by mechanistic biomarkers (B cell, DSA and biopsy features) at baseline, including more recently characterised complement-activating ability of DSA and AAMR gene expression biopsy signature.

Hypothesis 2: Although the clinical endpoint of TAR:GET-1 is graft loss, effective AAMR therapy will be reflected in changes in mechanistic features in serum and in biopsies. In the case of treatment with rituximab, this is achieved through favourable changes in B cell characteristics.

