3. STUDY DESIGN

Patient Cohort

This is a prospective cohort study using samples from all patients enrolled in the TAR:GET-1 (170 patients, 85 in each arm). The TAR:GET-1 trial will recruit patients starting in June 2019, over a period of 4 years, and patient will be followed up with further biological samples taken over a further period of 4 years. This will need to be analysed for which we estimate a further 2 years. The total duration of the study is therefore 10 years starting June 2019.

We aim to collect all samples from each patient to maximise the information obtained, whilst incurring negligible extra risk to the study participants.

Some of the samples are already obtained as part of the TAR:GET-1 protocol and we will use left over material to carry out analyses.

Some of the samples are not routinely obtained for TAR:GET-1 enrolment, but the TAR:GET-1 protocol and consent process covers their (optional) collection.

The only extra samples that requires a new consent process as part of M.O.T.-AMR is an optional post-treatment protocol biopsy.

The study aim is to be a comprehensive assessment of antibody-mediated rejection biomarkers pre- and post-treatment, but has below been artificially divided into Parts 1 and 2, Part 1 being funded by Imperial BRC, Cambridge BRC and NIHR EME (funding secured) whereas applications for funding for Part 2 are in process. A funding approval letter will be provided to the Sponsor and REC committee prior to commencing any element of part 2 of the study, and will specify which further specific elements of the study have received funding approval.

Samples taken as part of TAR:GET-1:

Patients enrolled in TAR:GET-1 will have a number of samples taken, and consent for enrolment in TAR:GET-1 includes agreement to the use of extra material left after diagnosis for research. We will therefore be able to access in 100% of patients enrolled in TAR:GET-1:

- Enrolment biopsy material
- Serum samples taken for DSA measurements
- Post-treatment indication biopsies taken as part of routine clinical care.

TAR:GET-1 is already assessing DSA MFI, DSA target and B lymphocyte numbers at baseline and 3 months post-treatment. In addition to these, M.O.T.-AMR will analyse in left over material from these routine samples:

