The additional samples are optional and M.O.T.-AMR is not dependent on them being obtained. As part of TAR:GET-1, patients will be offered the option of contributing extra tubes of blood at baseline, 3 months, 6 months and 1 year, and may decline any of them or all of them.

The extra samples will be: 1) lithium heparin tubes for PBMC isolation in order to carry out B cell immunophenotyping (flow cytometry); peripheral blood B cell stimulation assay (stimulation assay utilising intracellular staining for IL10 and IL6 and deriving a ratio to study regulatory potential of peripheral blood B cells)(Banham 2018)(extra tube of blood at 3 time points, fresh sample needed); and DNA analysis; and 2) PAXgene tubes for peripheral blood transcriptomics (whole blood transcriptomic analysis)(extra tube of blood at 3 time points).

Samples for 1) need to be shipped rapidly and we do not expect to take these samples until funding is secured, so estimate 50% of patients will contribute these, in the later stages of the trial. Samples for 2) can be frozen and batch-shipped so we expect them to be obtained in about 90% of patients.

Funding:

Part 1: Funding for taking and shipping of the PAXgene tubes will be covered by Cambridge BRC.

Part 2: We are applying for funding for the lithium heparin tube samples, and their collection will not be started until funding is secured. We are also applying for funding for the transcript analysis and DNA analysis.

Mechanistic Evaluation of Treatments for Acute Antibody-Mediated Rejection of the Kidney Transplant (M.O.T. AMR) – Version 1.4 27/05/2020

Optional post-treatment renal transplant protocol biopsy

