Specifically for M.O.T-AMR, patients enrolled in TAR:GET-1 will be offered an optional protocol biopsy at 6 months post-treatment. This additional sample is optional and M.O.T.-AMR is not dependent on it being obtained. This protocol biopsy will be carried out in the local centre, by the local clinical team. A post-treatment protocol biopsy is a biopsy taken in a patient with stable transplant function and no indication for a biopsy to be taken. The literature suggests that this a useful tool for monitoring response to treatment (Viglietti 2018a), but strong evidence from randomised controlled trials such as TAR:GET-1 is lacking for its routine introduction into clinical care and therefore, in most centres a post-treatment protocol biopsy is not offered to patients. The protocol biopsy will be collected for research and costed as research. Biopsy results on these protocol biopsies will be made available to the clinicians if any unexpected findings that need to be acted upon for patient benefit are noted. We will carry out the same histological and transcriptional investigations on these biopsies as for the enrolment and indication biopsies. A conservative estimate of protocol biopsy acceptance is 50%, based on our local experience (85 samples), and this is the number of samples we aim to achieve.

Funding:

Part 2: Funding for taking these biopsies is covered by NIHR EME 129029. Shipping and analysis will be partly covered by Imperial BRC.

This table illustrates how visits and samples in TAR:GET-1 will be used for investigations in M.O.T.-AMR. The additional samples needed for M.O.T.-AMR are in italic.

TAR:GET-1 trial visits	Baseline	Unscheduled	Visit 3 (month 3)	Visit 4 (month 6)	Visit 5 (month 12)
Biopsy histology and gene expression analysis	Use leftover sample	Indication biopsy for graft dysfunction: Use leftover samples		Optional protocol biopsy	
Serum DSA characteristics and BAFF	Use leftover sample		Use leftover sample		Use leftover sample
B cell characteristics and Peripheral blood transcriptomics	2 extra blood tubes		2 extra blood tubes	2 extra blood tubes	2 extra blood tubes

Sample storage:

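### Section 7 claims at least 90% power for any pathway biomarker, but two marker groups are expected in only about half of the 170 patients and the assumptions are not given

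*Protocol*

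**What the plan says.** Section 7 takes the cohort size from TAR:GET-1, 170 patients with 85 per arm, and then makes the protocol's only power statement. Its scope is set by these words: "Under plausible modelling assumptions, for any biomarker that is on the mechanistic pathway between treatment and primary outcome". What it promises for all such markers is that "the power of the main study (90%) will be matched or exceeded when comparing the mean biomarker values between treatment groups". The assumptions are not listed and no marker group is excepted.

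The same paragraph describes the mediation analysis as splitting the treatment effect into "a proportion attributable to a mechanism via the biomarker, and the complement attributable to direct effects, or other mechanisms".

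Section 3 gives these expectations for sampling:

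- Lithium-heparin tubes (B-cell immunophenotyping and stimulation assay) wait for funding, "so estimate 50% of patients will contribute these, in the later stages of the trial".
- For the 6-month protocol biopsy: "A conservative estimate of protocol biopsy acceptance is 50%, based on our local experience (85 samples". The section also makes 85 its target.
- PAXgene tubes can be frozen and shipped in batches, "so we expect them to be obtained in about 90% of patients".
- Leftover serum and enrolment biopsy tissue are to be accessible in all patients. In addition, "TAR:GET-1 is already assessing DSA MFI, DSA target and B lymphocyte numbers at baseline and 3 months post-treatment".

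**The concern.** The power figure stands beside the full cohort and covers every pathway marker, yet the protocol's own sampling estimates range from half of the patients to all of them. One figure cannot describe all of these comparisons.

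The primary objective in section 2 is the between-arm comparison of B-cell, antibody and tissue markers. Hypothesis 2 in section 1.2 places rituximab's effect in the B cells: "In the case of treatment with rituximab, this is achieved through favourable changes in B cell characteristics". The lithium-heparin assays supply most of the B-cell detail behind that hypothesis, and the protocol biopsy is the only scheduled post-treatment tissue. A reader who trusts 90% could take a null result in about 85 patients as evidence against the mechanism.

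**Working it through.** **The plan's own figure.** The 90% cannot be reproduced, because section 7 gives no effect size, SD, graft-loss rate or significance level for it. It can only be worked backwards. I assume a two-sided 5% two-sample t-test at one time point with equal arms; the two-sided 5% level matches the planned 95% confidence intervals.

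**Patients per marker group (section 3).** Leftover serum: 170. PAXgene: 0.90 × 170 = 153. Lithium-heparin assays and protocol biopsy: 0.50 × 170 = 85.

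**Detectable difference.** With *n* patients in total, the noncentrality parameter is d × √(n/4). Solving the noncentral t for 90% power gives d. The 95% interval half-width is t(0.975, n−2) × √(4/n).

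| n | d for 90% power (SD) | Power at d = 0.50 | Half-width of 95% CI (SD) |
|---|---|---|---|
| 170 | 0.500 | 90% | 0.30 |
| 153 | 0.527 | 87% | 0.32 |
| 85 | 0.711 | 62% | 0.43 |

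The normal approximation agrees: (1.960 + 1.282) × √(2/85) = 0.497 with 85 per arm, and that difference has 63% power with 42.5 per arm.

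**Baseline adjustment.** This multiplies d by √(1 − r²). With an assumed baseline correlation r = 0.5 the factor is 0.866, giving 0.43, 0.46 and 0.62 SD. The ratio of n = 85 to n = 170 stays at 0.711/0.500 = 1.42 for any common r.

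**Does being on the pathway guarantee 90%?** The protocol gives neither the total hazard ratio (HR) nor the graft-loss rate, so both are assumed. By Schoenfeld's formula, |ln HR| = 2 × 3.2415/√events for 90% power:

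- 40% graft loss, 68 events: 0.786, HR 0.46
- 50% graft loss, 85 events: 0.703, HR 0.495
- 70% graft loss, 119 events: 0.594, HR 0.55

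If a marker carries a given share of the effect, its between-arm difference is approximately share × |ln total HR| / ln(marker HR per SD).

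*One-third share, all 170 patients, total HR 0.495:*

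- marker HR 1.5: 0.234/0.405 = 0.58 SD, power 96%
- marker HR 2.0: 0.234/0.693 = 0.34 SD, power 59%
- marker HR 2.5: 0.234/0.916 = 0.26 SD, power 38%

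With a total HR of 0.45 these powers are 99%, 70% and 47%; with 0.55 they are 89%, 46% and 29%.

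*Full mediation, 85 patients, total HR 0.495:* the differences are 1.73, 1.01 and 0.77 SD, and power is above 99.9%, 99.6% and 94%.

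A separate linear mediation model, with the total effect set to 90% power at n = 170, points the same way. With half the effect mediated and a standardised marker-outcome path of 0.7, power is 63% at 170 and 36% at 85. With a path of 0.5 it is 90% and 63%.

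**The case against.** The strongest defence is that a marker truly on the pathway must differ between arms by more than the outcome does, so 90% for graft loss implies at least 90% for the marker. Under full mediation this largely holds, even at n = 85, as the last hazard-ratio calculation shows. But section 7 does not assume full mediation. It leaves room for direct effects and other mechanisms and plans an analysis of several biomarkers in parallel.

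Second, the 62% describes a marker chosen to sit exactly at 90% with 170 patients, whereas the protocol claims 90% or more. That is fair: 62% is the borderline case, not a prediction. The hazard ratios and mediated shares are also assumed; they show that the claim can fail, not that it will.

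Third, section 3 says the study does not depend on the optional samples, calls its 50% biopsy estimate conservative, and gives access to indication biopsies. The first point makes the study feasible without these samples but does not supply power for the markers they yield. Indication biopsies are unscheduled and come from patients with graft dysfunction, a selected subset.

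Fourth, the cohort size is set by TAR:GET-1 and no decision rule hangs on the power sentence. The planned 95% intervals will also show the imprecision afterwards. This limits the harm but leaves the planning figure unsupported.

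Finally, an SAP could list the assumptions. The unqualified figure is nevertheless fixed in this protocol.

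**Conclusion.** The concern holds. Nothing is miscalculated, since no inputs are shown; the fault is a power figure stated more broadly than the design supports. For the lithium-heparin assays and the protocol biopsy, the smallest difference detectable with 90% power is about 1.42 times that for the full cohort, and a marker that just reaches 90% at 170 has about 62%. PAXgene markers lose little (87%). Leftover-serum markers and the B lymphocyte counts made by TAR:GET-1 are untouched by the 50% figures. Even with all 170 patients, the words covering any biomarker need an assumption about the mediated share that the protocol does not state.

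The figures rest on a two-sided 5% t-test at one time point. The planned mixed models may shift the thresholds, but the protocol does not quantify this.

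**What to change.** In section 7:

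- Remove the wording that extends the claim to any biomarker, limit the 90% statement to markers available in the full cohort, and list its assumptions, including the mediated share.
- Give the detectable difference by marker group: about 0.50 SD for leftover serum (n = 170), 0.53 SD for PAXgene (n = 153) and 0.71 SD for the lithium-heparin assays and protocol biopsy (n = 85). Label these as single-time-point illustrations or recompute them for the planned mixed model.
- Note that 170 is a ceiling for serum, because section 8.2 requires separate consent for M.O.T.-AMR and section 4.4 withdraws patients who leave TAR:GET-1.
- State that a null comparison in about 85 patients does not exclude mediation.

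The cost is wording only. No patients or samples are added, and the stated figure becomes less favourable for the half-sampled markers.
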